### **9.2.1. Serious Adverse Events**

An SAE is any AE from this study that results in 1 of the following outcomes:

- death
- initial or prolonged inpatient hospitalization
- a life-threatening experience (that is, immediate risk of dying)
- persistent or significant disability/incapacity
- congenital anomaly/birth defect
- considered significant by the investigator for any other reason: important medical events that may not result in death, be life-threatening, or require hospitalization may be considered serious, based upon appropriate medical judgment.

Although all AEs occurring after signing the ICF are recorded in the eCRF, SAE reporting begins after the patient has signed the ICF and has received investigational product. However, if an SAE occurs after signing the ICF, but prior to receiving investigational product, it needs to be reported ONLY if it is considered reasonably possibly related to study procedure.

Study site personnel must alert Lilly or its designee of any SAE within 24 hours of investigator awareness of the event via a sponsor-approved method. If alerts are issued via telephone, they are to be immediately followed with official notification on study-specific SAE forms. This 24-hour notification requirement refers to the initial SAE information and all follow-up SAE information.

Pregnancy (during maternal or paternal exposure to investigational product) does not meet the definition of an AE. However, to fulfill regulatory requirements any pregnancy should be reported following the SAE process to collect data on the outcome for both mother and fetus.

Investigators are not obligated to actively seek AEs or SAEs in patients once they have discontinued and/or completed the study (the patient summary CRF has been completed). However, if the investigator learns of any SAE, including a death, at any time after a patient has been discharged from the study, and he/she considers the event reasonably possibly related to the study treatment or study participation, the investigator must promptly notify Lilly.

Requirements for the reporting of severe hypoglycemia episodes, AEs of pancreatitis, and AEs of systemic hypersensitivity as SAEs are found in Section 9.2.2.

#### **9.2.1.1. Suspected Unexpected Serious Adverse Reactions**

Suspected unexpected serious adverse reactions (SUSARs) are serious events that are not listed in the package insert and that the investigator identifies as related to investigational product or procedure. United States 21 CFR 312.32 and European Union Clinical Trial Directive 2001/20/EC and the associated detailed guidances or national regulatory requirements in participating countries require the reporting of SUSARs. Lilly has procedures that will be followed for the recording and expedited reporting of SUSARs that are consistent with global regulations and the associated detailed guidances.

### **9.2.2. Adverse Events of Interest**

#### **9.2.2.1. Hypoglycemia**

Patients will collect information on episodes of hypoglycemia between Visit 2 and the last study visit (Visit 13 or ET visit). For that purpose, patients will be trained about signs and symptoms of hypoglycemia, how to treat hypoglycemia, and how to collect appropriate information for each episode of hypoglycemia in the study diary (see Section 7.4.1.2) according to the Schedule of Activities (Section 2). Site personnel will enter this information into the eCRF at each visit after Visit 1.

### 9.2.2.2. Pancreatitis

Acute pancreatitis is defined as an AE of interest in all trials with dulaglutide, including this trial. Acute pancreatitis is an acute inflammatory process of the pancreas that may also involve peripancreatic tissues and/or remote organ systems (Banks and Freeman 2006). The diagnosis of acute pancreatitis requires 2 of the following 3 features:

1. Abdominal pain, characteristic of acute pancreatitis (generally located in the epigastrium and radiates to the back in approximately half the cases [Banks and Freeman 2006; Koizumi et al. 2006]; the pain is often associated with nausea and vomiting);
2. Serum amylase (total and/or pancreatic) and/or lipase  $\geq 3 \times \text{ULN}$ ; or
3. Characteristic findings of acute pancreatitis on computed tomography (CT) scan or magnetic resonance imaging (MRI).

If acute pancreatitis is suspected, appropriate laboratory tests (including levels of amylase [total and pancreatic] and lipase) should be obtained via the central laboratory (and locally, if needed). Imaging studies, such as abdominal CT scan with or without contrast, MRI, or gallbladder ultrasound, should be performed. If laboratory values and/or abdominal imaging supports the diagnosis of acute pancreatitis, the patient must discontinue therapy with investigational product and will also be discontinued from the study. The most appropriate diabetes therapeutic regimen will be decided by the investigator, based on the patient's clinical status. A review of the patient's concomitant medications should be conducted to assess any potential causal relationship with pancreatitis.

Each case of AE of pancreatitis must be reported. If typical signs and/or symptoms of pancreatitis are present and confirmed by laboratory values (lipase or amylase) and imaging studies, the event must be reported as an SAE. For a potential case that does not meet all of these criteria, it is up to the investigator to determine the seriousness of the case (AE or SAE) and the relatedness of the event to investigational product.

In addition to the diagnostic assessment in patients who develop symptoms of acute pancreatitis, each patient will have measurements of total amylase, lipase, and trypsin at Visit 3 (Week 0), Visit 7 (Week 16), Visit 10 (Week 36), Visit 12 (Week 52), and the 4-week safety follow-up visit to assess any potential effects of dulaglutide on the exocrine pancreas (refer to the Schedule of Activities, Section 2). Further diagnostic assessment per Lilly algorithm for assessment of asymptomatic pancreatic hyperenzymemia will be required whenever lipase and/or amylase (pancreatic and/or total) are  $\geq 3 \times \text{ULN}$  at any time during the study. If this situation occurs at Visit 12 (Week 52), the patient will undergo this additional work-up, and the data will be collected in the clinical trial database.

All AEs of acute or chronic pancreatitis, as well as cases of confirmed lipase or amylase values  $\geq 3 \times \text{ULN}$ , will be adjudicated by an independent committee of expert physicians. In addition, AEs of severe or serious abdominal pain of unknown origin will also be submitted to the

adjudication committee to assess for possible pancreatitis or other pancreatic disease. Relevant data from patients with acute or chronic pancreatitis, those with severe or serious abdominal pain, and those that undergo additional assessments due to confirmed hyperenzymemia will be entered into a specifically designed eCRF page by study site or Lilly staff. The adjudication committee representative will enter the results of adjudication in a corresponding eCRF page.

#### **9.2.2.3. C-Cell Hyperplasia and C-Cell Neoplasms**

Individuals with personal or family history of certain thyroid or nonthyroid endocrine abnormalities or certain preexisting laboratory and genetic characteristics will be excluded from the study (see Section 6.2). The assessment of thyroid safety during the trial will include reporting of thyroid treatment-emergent adverse events (TEAEs) and measurements of calcitonin according to the Schedule of Activities (Section 2) at Visit 1, Visit 3 (Week 0), Visit 7 (Week 16), Visit 10 (Week 36), and Visit 12 (Week 52). The purpose of calcitonin measurements is to assess the potential of dulaglutide versus placebo to affect the thyroid C-cell function, which may indicate development of C-cell hyperplasia and neoplasms.

Patients who develop serum calcitonin increases  $\geq 50\%$  of the mean of the baseline and screening values AND an absolute value  $\geq 20$  pg/mL and  $< 35$  pg/mL at Visit 12 (Week 52) will be asked to repeat the measurement within 1 month. If this repeat value is increasing ( $\geq 10\%$  increase), it will be recommended that the patient undergo additional endocrine assessment and longer-term follow-up by an endocrinologist to exclude a serious adverse effect on the gland.

Patients with an increase in serum calcitonin  $\geq 50\%$  of the mean of the baseline and screening values AND an absolute value  $\geq 35$  pg/mL at Visit 12 (Week 52) will be recommended to immediately undergo additional endocrine assessments and longer-term follow-up by an endocrinologist.

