Laboratory tests will be performed at Visit 1. A telephone visit (T/V1; or site visit if preferred by the patient) at Week -12 will occur after Visit 1 laboratory results are available, and eligible patients on dipeptidyl peptidase-4 (DPP-4) inhibitors, SU, or glinides will begin a 12-week washout period during which the insulin dose may be uptitrated for up to 4 weeks, with an 8 week-stabilization ( $\pm$  20% adjustment) prior to Visit 3. During Weeks -8 through 0 (the insulin dose stabilization period), a second telephone visit (T/V2; or site visit, if preferred) may occur. The insulin dose should remain unchanged for the 16-week primary treatment period, unless hypoglycemia occurs (see Section 7.4.1.2). In addition, for patients treated with 1 or 2 OADs other than DPP-4 inhibitors, SU, or glinide prior to Visit 1, the dosage and administration of OADs should not be changed during the 16-week primary treatment period. Eligible patients not on DPP-4 inhibitors, SU, or glinides can proceed to Visit 2. At Visit 2, HbA1c will be measured and eligibility will be reconfirmed. At Visit 3, approximately 160 patients will be randomized in a 3:1 ratio to dulaglutide 0.75 mg or placebo. After 16 weeks of primary treatment period, patients taking placebo will be switched to dulaglutide for an additional 36 weeks of extension treatment period. After the extension treatment period, dulaglutide must be discontinued and restart is not allowed during the follow-up period. To preserve the blinding of the study, the treatment assignments in the double-blind primary treatment period will be blinded to patients and investigators until study completion.

Figure GBGF.1 illustrates the study design.

Abbreviations: DPP-4i = dipeptidyl peptidase-4 inhibitors; Dula = dulaglutide; F/U = follow-up; IC = informed consent; n = number of patients; OAD = oral antidiabetic; Plc = placebo; SU = sulfonylurea; T/V = telephone visit; wks = weeks.

Note: A telephone visit (T/V1; or site visit if preferred) will occur at Week -12 after screening results are available. An optional telephone visit (T/V2; or site visit if preferred) may occur between Weeks -8 and 0. Telephone visits or site visits may occur anytime during the study, as needed.

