- [25] have any self or family history of medullary C-cell hyperplasia, focal hyperplasia, or carcinoma (including sporadic, familial, or part of MEN 2A or 2B syndrome);
- [26] have serum calcitonin  $\geq$ 20 pg/mL, as determined by the central laboratory at Visit 1;
- [27] have evidence of a significant, active uncontrolled endocrine or autoimmune abnormality, as judged by the investigator at Visit 1;
- [28] have a history of transplanted organ;
- [29] have a history of active or untreated malignancy, or are in remission from a clinically significant malignancy during the 5 years prior to Visit 1;
- [30] have a history of any other condition which, in the opinion of the investigator, may preclude the participant from following and completing the protocol;
- [31] have any hematologic condition that may interfere with HbA1c measurement (for example, hemolytic anemias, sickle-cell disease);
- [32] are currently enrolled in any other clinical trial involving an investigational product or any other type of medical research judged not to be scientifically or medically compatible with this study
- [33] have participated, within the last 30 days in a clinical trial involving an investigational product. If the previous investigational product has a long half-life, 3 months or 5 half-lives (whichever is longer) should have passed;
- [34] have previously completed or withdrawn from this study or any other study investigating dulaglutide;

[35] are investigator site personnel directly affiliated with this study and/or their immediate families. Immediate family is defined as a spouse, parent, child, or sibling, whether biological or legally adopted;

[36] are Lilly employees;

[37] are unable and/or unwilling to provide written informed consent, make themselves available for the duration of the study, or abide by study procedures and restrictions.

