### **9.4.5. Safety Monitoring**

Lilly will periodically review evolving aggregate safety data within the study by appropriate methods.

In addition, specific safety measures are included in the protocol to ensure appropriate monitoring of pancreatic, thyroid, and liver safety. Laboratory findings that trigger pancreatic and thyroid safety monitoring per Lilly standards are provided in Sections 9.2.2.2 and 9.2.2.3, respectively. If a study patient/subject experiences elevated ALT  $\geq 3X$  ULN, ALP  $\geq 2X$  ULN, or elevated TBL  $\geq 2X$  ULN, clinical and laboratory monitoring should be initiated by the investigator. Details for hepatic monitoring depend upon the severity and persistence of observed laboratory test abnormalities. To ensure patient safety and to comply with regulatory guidance, the investigator is to consult with the Lilly CRP or CRS regarding collection of specific recommended clinical information and follow-up laboratory tests (see [Appendix 4](#)).

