#### 5.14.4.2. Calcitonin

Threshold analyses will be performed for calcitonin. Some of these analyses involve a composite criterion involving change from baseline of at least 50%. For alignment with the calcitonin monitoring algorithm used in study, the baseline value for this analysis will be the mean of all nonmissing baseline observations. In cases where baseline is missing but postbaseline is available, the percent-change criterion will be assumed to be satisfied. Following threshold analyses will be provided:

- postbaseline calcitonin  $\geq 20$  pg/mL
- postbaseline calcitonin  $\geq$  35 pg/mL

Additionally, for each of these, a threshold analysis will be presented of patients also satisfying a change from baseline of  $\geq$ 50%.

A shift table will be provided of postbaseline calcitonin to and from the following categories: (i) <20 pg/mL, (ii)  $\geq 20 \text{ pg/mL}$  and <35 pg/mL, (iii)  $\geq 35 \text{ pg/mL}$ .

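### Both calcitonin responses in Protocol 9.2.2.3 are tied to Week 52, so a qualifying value at Week 16, Week 36 or early termination triggers no specified expedited repeat or referral

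*Protocol*

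**What the plan says.** The Schedule of Activities (Protocol Section 2) marks calcitonin at Visit 1, Visit 3 (Week 0), Visit 7 (Week 16), Visit 10 (Week 36), Visit 12 (Week 52) and ET. It does not mark Visit 13. The visit list in Section 9.2.2.3 omits ET, but the Schedule includes it.

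Section 9.2.2.3 gives two responses. Each requires a rise of at least 50% over the mean of the screening and baseline values.

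- Value from 20 to below 35 pg/mL: the patient "at Visit 12 (Week 52) will be asked to repeat the measurement within 1 month". If the repeat is at least 10% higher, endocrine assessment and longer follow-up are recommended.
- Value of 35 pg/mL or more: the patient "at Visit 12 (Week 52) will be recommended to immediately undergo additional endocrine assessments and longer-term follow-up by an endocrinologist".

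Section 9.4.5 names this as the place for the thyroid rule: "Laboratory findings that trigger pancreatic and thyroid safety monitoring per Lilly standards are provided in Sections 9.2.2.2 and 9.2.2.3, respectively".

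The neighbouring pancreatic enzyme rule in Section 9.2.2.2 applies "at any time during the study. If this situation occurs at Visit 12 (Week 52), the patient will undergo this additional work-up". Here Week 52 is an added case of a rule that already covers every visit.

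**The concern.** The same laboratory result is handled differently according to the visit at which it appears. A value of 35 pg/mL or more with a 50% rise leads to a recommendation for immediate endocrine assessment at Week 52. At Week 16, Week 36 or ET the protocol specifies nothing for it.

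The stake is patient safety: how soon a suspicious value is repeated or referred. Section 8.1.1 requires discontinuation once C-cell hyperplasia or medullary thyroid carcinoma is diagnosed. The only calcitonin-triggered work-up that could lead to such a diagnosis starts at Week 52, when treatment ends. For a patient who leaves early, ET is the last calcitonin measurement, and no response is attached to it.

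**Working it through.** The plan states no figure to reproduce here. The check sets sampling points against responses and then works out the intervals.

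**Step 1. Sampling points against responses** (Schedule of Activities; Section 9.2.2.3).

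| Post-baseline draw | Response specified? | Next scheduled calcitonin |
|---|---|---|
| Visit 7 (Week 16) | No | Visit 10 |
| Visit 10 (Week 36) | No | Visit 12 |
| Visit 12 (Week 52) | Yes, both | None |
| ET | No | None |

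One of four post-baseline sampling points carries a response.

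**Step 2. Time to the next scheduled draw.** Nominal days are week × 7: Visit 7 = 112, Visit 8 = 140, Visit 10 = 252, Visit 11 = 308, Visit 12 = 364. Each visit has a window of ±7 days, so an interval between two visits varies by ±14 days.

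- Visit 7 to Visit 10: 252 − 112 = 140 days, range 126 to 154, which is 20 weeks (18 to 22).
- Visit 10 to Visit 12: 364 − 252 = 112 days, range 98 to 126, which is 16 weeks (14 to 18).
- ET: no later calcitonin draw.

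The Visit 10 draw carries no response either. For a Week 16 value, the first scheduled draw that can trigger one is therefore Week 52, which is 52 − 16 = 36 weeks later, and only if the value still qualifies then. The Week 52 rule itself asks for a repeat within 1 month, or immediate assessment.

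**Step 3. Is there another calcitonin trigger?**

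- Section 6.2 excludes C-cell history and a Visit 1 calcitonin of 20 pg/mL or more. This acts at entry only.
- Section 8.1.1 allows discontinuation by investigator decision and requires it on a C-cell diagnosis. It names no calcitonin value.
- Section 8.1.2 permits temporary interruption. It sets no threshold, repeat or referral.
- Section 9.2 requires documented review of each laboratory safety report. It sets no threshold.
- Section 9.4.3 covers AE reporting when a significant finding results in a diagnosis. It specifies no repeat or referral.
- Section 9.4.5 refers back to 9.2.2.3 for thyroid. The hepatic triggers in the same section have no visit limit.
- SAP 5.14.4.2 tabulates post-baseline values at 20 and 35 pg/mL, and for each cut-off "a threshold analysis will be presented of patients also satisfying a change from baseline of" at least 50%. It is not limited to Week 52, but it is a reporting table and directs no patient care.

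None of these sets a calcitonin trigger during treatment or at ET.

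**Step 4. Can existing visits take the repeat?**

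- After Visit 7: Visit 8 is 140 − 112 = 28 days later, range 14 to 42.
- After Visit 10: Visit 11 is 308 − 252 = 56 days later, range 42 to 70, which is beyond 1 month.
- After ET: ET falls 0 to 14 days after the decision to stop and Visit 13 falls 28 ± 7 days after it, so the gap is 21 − 14 = 7 to 35 − 0 = 35 days.

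**The case against.** The best defence is that Week 52 was chosen deliberately as an end-of-treatment handoff. Section 9.2.2.3 describes calcitonin sampling as a comparison of dulaglutide with placebo, and Visit 12 is a completer's last draw. In the meantime investigators are responsible for medical care, follow medically important AEs, examine the patient at every visit and may add visits. The sponsor reviews aggregate safety data, and the SAP expects unscheduled laboratory results. Nothing tells anyone to wait after a high value.

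Much of this stands, and it lowers the consequence. It does not close the gap. The protocol does not give the handoff as its reason, ET is equally a last draw, and a handoff does not explain why a value of 35 pg/mL or more calls for immediate assessment at one visit only.

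Some stronger readings are tempting but unsupported:

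- *That no repeat is ever scheduled.* Draws follow at Weeks 36 and 52. What is missing is an expedited repeat or a referral. Only ET has no later draw.
- *That the gap costs additional doses.* Neither Week 52 response holds the drug. Interruption stays with the investigator under Section 8.1.2, before and after the fix.
- *That a Week 16 rule would stop placebo patients from starting dulaglutide.* Section 5.1 says "patients taking placebo will be switched to dulaglutide for an additional 36 weeks", but extension product is dispensed at the visit where the sample is drawn for the central laboratory. The documents give no turnaround time, so a result before dispensing cannot be assumed.
- *That any later value of 35 pg/mL or more must qualify.* The exclusion applies to a value of at least "20 pg/mL, as determined by the central laboratory at Visit 1", whereas the rule compares with the mean of screening and baseline. As an invented illustration, 19 at Visit 1 and 30 at Visit 3 give a mean of 24.5. A later 35 is then a rise of 35/24.5 − 1 = 43%, short of 50%.
- *That the SAP contradicts the protocol.* Its phrase "For alignment with the calcitonin monitoring algorithm used in study" explains the choice of baseline value. Counting all post-baseline values in a table does not conflict with a narrower action rule.

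**Conclusion.** The concern holds as a patient-safety gap in the wording of Section 9.2.2.3. Three of the four post-baseline calcitonin sampling points have no specified response. After a qualifying Week 16 or Week 36 value, the next scheduled measurement is about 20 weeks (18 to 22) or 16 weeks (14 to 18) away. After ET there is none. The strongest cases are a qualifying value at ET and a value of 35 pg/mL or more with a 50% rise at any visit before Week 52.

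The number of patients affected cannot be estimated, because the documents give no frequency of qualifying values. The entry exclusions should make them less common in a trial of about 160 patients. The conclusion assumes that no separate thyroid algorithm applies, which is how Section 9.4.5 reads. The primary analysis, power and alpha are untouched. It should be fixed because the change is small and the result in question is one the protocol itself treats as urgent at Week 52.

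**What to change.** In both response paragraphs of Section 9.2.2.3, replace the Visit 12 (Week 52) restriction with *at any scheduled post-baseline measurement (Visit 7, Visit 10, Visit 12 or ET)*. Keep the thresholds, the comparator and the responses as they are. Leave the decision to interrupt study drug with the investigator under Section 8.1.2. The SAP needs no change.

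The cost is one wording amendment and a few extra repeat samples or referrals. No routine draw is added. A repeat after Visit 7 can often be taken with the blood draw at Visit 8, and one after ET with the draw at Visit 13. A qualifying Visit 10 value needs an unscheduled sample. So does a Visit 7 or ET value when the windows put the next visit more than 1 month away.

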#### **9.2.2.4. Cardiovascular Events**

Deaths and nonfatal cardiovascular (CV) AEs will be adjudicated by a committee of physicians external to Lilly with cardiology expertise. The nonfatal CV AEs to be adjudicated include: MI; hospitalization for unstable angina; hospitalization for heart failure; coronary interventions (such as coronary artery bypass graft or percutaneous coronary intervention); and cerebrovascular events, including cerebrovascular accident (stroke) and transient ischemic attack (TIA).

